# 1 PROTOCOL SYNOPSIS

- Primary Objective:** To evaluate the incidence of complications resulting from far lateral spine surgery utilizing the K2M RAVINE® Lateral Access System (RAVINE) with ALEUTIAN® Lateral Interbody Spacer System or CASCADIA® Lateral Interbody Spacer System versus literature reported results for the NuVasive XLIF® system (XLIF) in the treatment of degenerative disc disease (DDD) with up to Grade 1 spondylolisthesis.
- Study Design:** Prospective, non-randomized (single-arm) multi-center study
- Follow-Up Evaluations:** Clinical evaluations of patients implanted with ALEUTIAN or CASCADIA using the RAVINE system will be conducted at initial post-op, 3 months, 6 months, 12 months and 24 months post-procedure. Adverse events will be monitored continuously.
- Effectiveness Assessment:** Effectiveness measurements include the following:
- Back, Hip/Buttock, and Leg Pain 10cm Visual Analog Scale (VAS)
  - Evaluation of the Incidence of Thigh Pain and Dysesthesia
  - Quantitative and Qualitative Radiographic Assessments
    - Fusion Assessment
    - Device Status
  - Oswestry Low Back Pain Disability Index (ODI)
  - SF-12v2 Health Survey, including SF-6D Utility Index assessment
  - Patient Satisfaction
  - Odom's Criteria
  - Perioperative Assessments
    - Surgery Time
    - Anesthesia Times
    - Estimated Blood Loss
    - Neuromonitoring
  - Length of Hospital Stay
  - Return to Work/School
  - Use of Narcotics Post-Surgery
- Safety Assessment:** Safety will be assessed by:
- The evaluation of all adverse events including device related, procedure related and additional serious adverse events.
  - Additional surgical intervention at the operative site including the need for removals, revisions, re-operations or supplemental fixation required to modify the device
  - The incidence and severity of any psoas muscle injury, genital femoral nerve injury and lumbar plexus injury will be determined for all patients
- Study Subjects:** Patients eligible for study enrollment will have a primary diagnoses limited to degenerative disc disease (DDD) with up to Grade 1 spondylolisthesis at L2-S1 requiring surgical intervention at one or two contiguous levels. Qualified patients

will have confirmed failure of conservative therapy as well as plain film imaging studies. Subjects must be  $\geq 18$  years old at the time of enrollment.

**Device Evaluation Group:** K2M RAVINE Lateral Access System with ALEUTIAN Lateral Interbody Spacer System cleared for marketing and distribution under 510(k) K113138 or K2M RAVINE Lateral Access System with CASCADIA Lateral Interbody Spacer System cleared for marketing and distribution under 510(k) K150480.

**Comparative Group:** Historical, literature control of reported results with the use of the NuVasive XLIF system for far-lateral spinal stabilization.

**Sample Size:** Two-hundred twenty-two (222) total subjects at up to 15 clinical sites. Sites are considered a Principal Investigator and their Sub-Investigators who are covered by a single Institutional Review Board's (IRB's)/Ethics Committee's (EC's) oversight and approval.

Subject enrollment will be capped so that no single site contributes more than approximately 20% of cases.

**Investigator Selection:**

- Appropriate patient population for trial indication
- An investigator must have completed a minimum of three surgeries using the RAVINE system. If a surgeon does not have experience in using the RAVINE system, their first three (3) patients will be considered roll-in patients and the results from these patients will be analyzed against the entire cohort to determine if a learning curve exists. If a surgeon has previously completed three (3) surgeries using the Ravine system, there will be no stratification of their data.
- Experience in clinical trial execution
- Dedicated research infrastructure
- Local institutional review board (IRB)/Ethics Committee (EC) for research oversight or ability to use central IRB/EC
- Standard of Care (SOC) compatible with or capable of complying with the protocol requirements including but not limited to:
  - Neurological assessment, with specific evaluation of the incidence of thigh pain and/or dysesthesia after surgery
  - Use/Collection of patient reported outcome measures – ODI; Back, Hip/Buttock, and Leg VAS; SF-12v2
  - Follow-up evaluations at initial post-op, 3 months, 6 months, 12 months, and 24 months
- Insofar as possible, sites for the study will be distributed regionally and by type of institution and level of investigator experience, patient volume and research experience so that any unanticipated and potentially prognostic factors may then be balanced both geographically and demographically in the study.

## 2 INTRODUCTION

### 2.1 Study Purpose

The purpose of this study is to evaluate the complication rate of the RAVINE Lateral Access System with the ALEUTIAN Lateral Interbody Spacer System or the CASCADIA Lateral Interbody Spacer System compared to the literature reported results with the NuVasive XLIF® system, with particular interest in the incidence of thigh/leg pain and dysesthesia.

### 2.2 Background and Significance

Degenerative disc disease is a spinal condition caused by the breakdown of intervertebral discs. As a result of aging, the spine begins to show signs of wear and tear as the discs dry out and shrink. These age-related changes can lead to arthritis, disc herniation, or spinal stenosis, which can put pressure on the spinal cord and nerves and may cause back pain. Spinal fusion is often utilized as the final treatment after conservative method attempts have failed.

Minimally invasive (MI) fusion surgeries have been developed to treat disorders of the spine with less disruption to the muscles. This can result in quicker recovery, decreased operative blood loss, and the speed that patients return to normal function. While most MI access systems maintain the common table-mounting design, spine-fixed retractors provide stabilization of the exposure irrespective of patient movement on the operating table. Without the threat of compromising the surgical field through a disturbance in patient position, the retractors can shift relative to the patient and therefore potentially reduce complications associated with retractor placement and pressure.

### 2.3 Device Description

The RAVINE Lateral Access System (K2M, Leesburg, VA) is a far-lateral, spine-fixed dual blade retractor system that allows for a muscle splitting transpoas approach. Used in conjunction with the ALEUTIAN Lateral Interbody Spacer System or the CASCADIA Lateral Interbody Spacer System, an anterior fusion can be established with potentially less post-operative neurological and muscle damage. If required, supplemental stabilization can be achieved utilizing the K2M SERENGETI® Minimally Invasive Retractor System, a flexible percutaneous delivery system that allows for direct visualization and access to the posterior screw heads for simple rod insertion of the K2M DENALI® Spinal System, K2M EVEREST® Spinal System, or K2M EVEREST® MI XT Spinal System. Alternatively, supplemental fixation can be achieved utilizing the K2M CAYMAN® Minimally Invasive Plate System, a low profile plate and screw system specifically designed for insertion through the RAVINE Lateral Access System's true muscle-splitting Retractor.

The ALEUTIAN Lateral Interbody Spacer System was cleared for marketing under 510(k) K113138 and the CASCADIA Lateral Interbody Spacer System was cleared for marketing under 510(k) K150481. The surgical technique guides for both interbody spacer systems include the RAVINE Lateral Access Retractor System as instrumentation (Class I). The SERENGETI Minimally Invasive Retractor System was included in the surgical technique guide for the DENALI Minimally Invasive Screw System, cleared under 510(k) K112037. The EVEREST Spinal System was cleared for marketing under 510(k) K103440. The CAYMAN Minimally Invasive Plate System was cleared for marketing under 510(k) K131533. The EVEREST MI XT Spinal System was cleared for marketing under 510(k) K151727.

### 2.4 Surgical Procedure

The implantation using the RAVINE system should be performed according to the standard of care of the Investigator, and in accordance with K2M's Instructions for Use and Surgical Technique Manual for the RAVINE Lateral Access System with the ALEUTIAN Lateral Interbody Spacer System or the CASCADIA Lateral Interbody Spacer System. Supplemental stabilization with either the SERENGETI Minimally Invasive Retractor System or the CAYMAN Minimally Invasive Plate System, if required, should be performed according to the Instructions

for Use provided by K2M. RAVINE cases utilizing minimally invasive (percutaneous or mini-open) supplemental fixation with facet screws or competitive pedicle screw, thoracolumbar plate systems, if required, should be performed according to the Instructions for Use of the manufacturer.

## 2.5 Indications for Use

The RAVINE system is to be used for far lateral access to the spine for surgical interventions indicated for the use of ALEUTIAN Lateral or CASCADIA Lateral implants. When used as a lumbar intervertebral body fusion device, the ALEUTIAN Lateral and CASCADIA Lateral implants are indicated for spinal fusion procedures to be used with autogenous bone graft in skeletally mature patients. The lumbar IBF implants are intended for use at either one level or two contiguous levels in the lumbar spine, from L2 to S1, for the treatment of degenerative disc disease (DDD) with up to Grade 1 spondylolisthesis. DDD is defined as back pain of discogenic origin with degeneration of the disc confirmed by history and radiographic studies. The lumbar device is intended to be used in patients who have had six months of non-operative treatment.

In the cases where a supplemental stabilization is necessary after the anterior placement of the IBF implant, the SERENGETI Minimally Invasive Retractor System or the CAYMAN Minimally Invasive Plate System can be utilized. The SERENGETI system is a disposable set of surgical access devices for use only in conjunction with the DENALI Minimally Invasive Spinal System or the EVEREST Degenerative Spinal System. The DENALI and EVEREST systems are non-cervical spinal fixation devices intended for posterior, non-pedicle fixation for DDD and spondylolisthesis among other indications outside the scope of this study. The CAYMAN Minimally Invasive Plate System is a low profile plate and screw system specifically designed for insertion through the RAVINE Lateral Access System's true muscle-splitting Retractor. The CAYMAN Minimally Invasive Plate System is indicated for use via the lateral or anterolateral surgical approach in the treatment of thoracic and thoracolumbar (T1-L5) spine and for use as an anteriorly placed supplemental fixation device for the lumbosacral level below the bifurcation of the vascular structures (L5-S1).

## 2.6 Benefits and Risks

### 2.6.1. *Potential Benefits*

There is no guarantee that the subject will experience any immediate or direct benefits with the use of this device system or for taking part in this study.

### 2.6.2. *Potential Risks*

Potential risks identified with the use of this device system include those associated with any spinal surgery resulting in neurological, cardiovascular, respiratory, gastrointestinal, or death. Additionally, with the use of a far lateral access system, potential risks also include those associated with the inherent psoas muscle splitting accompanying such an approach; particularly thigh pain, dysesthesia, and neurological complications.

A full listing of potential risks of the device and the surgical procedure can be found in **Section 9.5 Potential Risks and Anticipated Adverse Events**.

## 2.7 Mitigation of Risks

Operative and acute periprocedural risks for the patients enrolled in this study are mitigated by restricting the use of the device to skilled neurological and orthopedic spine surgeons trained and experienced in the proper surgical technique to implant the respective devices. Long-term risks such as device migration/failure and pseudoarthrosis are mitigated by proper patient selection and implanting the devices in accordance with the Surgical Technique

Manuals for the ALEUTIAN Lateral Interbody Spacer System or the CASCADIA Lateral Interbody Spacer System, the RAVINE and the SERENGETI or CAYMAN Minimally Invasive Plate System (if applicable) systems and the use of the surgical instruments provided by K2M; and by following accepted standard care in this population for far lateral fusion surgery.

CONFIDENTIAL DO NOT COPY

### 3 INVESTIGATOR/SITE SELECTION

The investigators selected to participate in this clinical study will be responsible for conducting the study according to the requirements of the protocol. Each site will have a designated Principal Investigator and may have Sub-Investigators. Investigators/sites will be selected for participation in the study according to the following criteria:

The Investigator/Site must have:

- Expertise in clinical areas relevant to the study, including a background in spine surgery, sufficient experience in clinical research and an adequate patient population with adult spine disorders
- Completed a minimum of three (3) surgeries using the RAVINE system. If a surgeon does not have experience in using the RAVINE system, their first three (3) patients will be considered roll-in patients and the results from these patients will be analyzed against the entire cohort to determine if a learning curve exists. If a surgeon has previously completed three (3) surgeries using the Ravine system, there will be no stratification of their data.
- Experience in participating in clinical studies and have adequate personnel and a dedicated research infrastructure including a Study Coordinator to adequately perform the tasks required by the clinical protocol
- Local institutional review board (IRB)/Ethics Committee (EC) for research oversight or ability to use central IRB/EC
- A practice in a medical facility equipped appropriately to fulfill the surgical and patient contact requirements of the study
- A standard of care (SOC) compatible with or capable of complying with the protocol requirements including but not limited to:
  - Neurological assessment, with specific evaluation of the incidence of thigh pain and/or dysesthesia after surgery
  - Use/Collection of patient reported outcome measures – ODI; Back, Hip/Buttock, and Leg VAS; SF-12v2
  - Follow-up evaluations at initial post-op, 3 months, 6 months, 12 months, and 24 months
- (Be willing to) sign a Clinical Research Agreement and abide by the agreement for the duration of the study.
- (Be willing to) provide financial disclosure; including updating the disclosure during the study if the financial status changes.

Insofar as possible, sites for the study will be distributed regionally and by type of institution and level of investigator experience, patient volume and research experience so that any unanticipated and potentially prognostic factors may then be balanced both geographically and demographically in the study.

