### 4.4 Sample Size

Two-hundred twenty-two (222) total subjects at up to 15 clinical sites. Sites are considered a Principal Investigator and their Sub-Investigators who are covered by a single Institutional Review Board's (IRB's)/Ethics Committee (EC) oversight and approval.

Subject enrollment will be capped so that no single site contributes more than approximately 20% of cases.

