### 12.3 Sample Size

A total sample size of 222 subjects was selected for the study. Assuming the true mean difference between pre-op and 24 month follow-up VAS is 3.66 and the standard deviation is 2.0, a sample size of 189 subjects provides >87% power to detect a statistically significant difference between the mean post-op VAS and the OPC of 3.25 using a one-sided one-sample t-test at a significance level of 0.05. In order to account for approximately 15% attrition, based on clinical experience, 222 subjects will be enrolled.

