### 12.4 Analysis Populations

Analysis Populations are defined as follows:

- The Intent-to-Treat (ITT) population includes all enrolled subjects.
- The Per-Protocol population includes all enrolled subjects who have no major protocol violations (defined as not meeting inclusion/exclusion criteria or not being consented properly) and have 24 month VAS scores.

The effectiveness analysis will be performed on the Per Protocol population. Analysis of the ITT population considering several missing data imputations will be confirmatory of the Per Protocol analysis. Safety summaries will be performed on the ITT population.

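### The learning-curve check compares roll-in patients with a cohort that, as worded, includes them, so any difference it shows is diluted

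*Combined protocol and SAP*

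**What the plan says.** The investigator-selection text, given in the same words in the Section 1 synopsis and in Section 3, asks for at least three prior RAVINE surgeries. Where a surgeon lacks that experience, the first three study cases are labelled roll-ins. The use to be made of those cases is stated in one clause: "the results from these patients will be analyzed against the entire cohort to determine if a learning curve exists". For surgeons who already have three cases, "there will be no stratification of their data".

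The number of roll-ins is not stated. Section 4.4 plans "Two-hundred twenty-two (222) total subjects at up to 15 clinical sites", and Section 3 adds that "Each site will have a designated Principal Investigator and may have Sub-Investigators", so the number of surgeons is open as well.

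Section 8.1 counts a patient as enrolled once consent is signed. Section 12.4 then says: "The Intent-to-Treat (ITT) population includes all enrolled subjects". The Per-Protocol population removes subjects with major violations, "defined as not meeting inclusion/exclusion criteria or not being consented properly", and those without a 24-month VAS score. Neither definition mentions roll-in status. Section 12 does not mention the learning-curve comparison and gives it no endpoint, test, significance level or decision rule.

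**The concern.** A learning-curve check asks whether a surgeon's first cases do worse than cases done with experience. The natural contrast is between two groups with no patient in common. If the reference group is the whole cohort, and the roll-ins belong to it, they are partly compared with themselves. The reference mean is pulled towards the roll-in mean and the gap shrinks. The shrinkage is always towards no difference, which is the wrong direction for a check meant to reveal one.

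This matters because the purpose in Section 2.1 is the complication rate, with particular interest in thigh or leg pain and dysesthesia. Section 2.7 also relies on trained and experienced surgeons to limit operative risk. This comparison is the only analysis the documents describe that looks at early cases separately. If it understates the difference, readers will underestimate what inexperience costs.

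**Working it through.** **Inputs from the documents.** Enrolment 222 and up to 15 sites (Section 4.4); three roll-ins per new surgeon (Section 3); SD of VAS change 2.0, assumed mean improvement 3.66, criterion 3.25, 189 evaluable subjects, about 15% attrition (Section 12.3).

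**Inputs assumed here.** Number of roll-ins m = 3, 15, 45 or 90, that is 1, 5, 15 or 30 new surgeons; m = 45 is one new surgeon at each of 15 sites and m = 90 is two. A true roll-in versus non-roll-in difference of 1.0 VAS point, and two-sided 0.05, are used only for the testing illustration. Roll-ins are taken to count in the 222.

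**Step 1: the plan's own figure.** Section 12.3 states: "Assuming the true mean difference between pre-op and 24 month follow-up VAS is 3.66". The effect is 3.66 − 3.25 = 0.41. The standardised effect is 0.41 / (2.0/√189) = 2.82. One-sided 0.05 power is 88.0% by the normal approximation and 87.8% by the noncentral t, in agreement with the stated >87%. Enrolment is 189/0.85 = 222.4, which matches 222. The plan gives no figure for the learning-curve check.

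**Step 2: dilution.** The cohort mean is (m/N) × mean(roll-in) + (1 − m/N) × mean(rest). Therefore

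mean(roll-in) − mean(all) = (1 − m/N) × [mean(roll-in) − mean(rest)].

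The same holds for proportions, and it does not depend on any test. With N = 222:

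| m | 1 − m/N | Shrinkage |
|---|---|---|
| 3 | 0.99 | 1.4% |
| 15 | 0.93 | 6.8% |
| 45 | 0.80 | 20.3% |
| 90 | 0.59 | 40.5% |

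**Step 3: what follows if the groups are treated as independent.** The true variance of the overlapping contrast is SD²(1/m − 1/N). An ordinary two-sample test would use SD²(1/m + 1/N). For m = 45, N = 222, SD = 2.0:

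- assumed SE = 2.0 × √(1/45 + 1/222) = 0.327
- true SE = 2.0 × √(1/45 − 1/222) = 0.266
- effective critical value = 1.96 × 0.327/0.266 = 2.41, so the real type I error is about 1.6%
- expected contrast for a 1.0-point difference = 0.797; 0.797/0.266 = 2.99; power about 72%
- disjoint SE = 2.0 × √(1/45 + 1/177) = 0.334; 1.0/0.334 = 2.99; power about 85%

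The same calculation for each m:

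| m | Type I error, overlapping | Power, overlapping | Power, disjoint |
|---|---|---|---|
| 3 | 4.7% | 13% | 14% |
| 15 | 3.6% | 41% | 46% |
| 45 | 1.6% | 72% | 85% |
| 90 | 0.3% | 74% | 96% |

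Simulated t-tests (20,000 runs per setting, for m = 15, 45 and 90) gave closely similar values, for example 1.5%, 71% and 85% for m = 45.

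**Step 4: what follows if the overlap is allowed for.** The two ratios of 2.99 in Step 3 are equal. With the correct variance the overlapping contrast carries the same test statistic as the disjoint one, and no power is lost. The raw difference is still reported at 80% of its true size.

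**Step 5: the evaluable set.** About 189 subjects are expected to have a 24-month VAS. If attrition is equal in both groups, m/N does not change: 45 × 0.85 is about 38, and 1 − 38/189 = 0.80. Power is then about 64% for the overlapping comparison treated as independent and about 79% for the disjoint one, a similar gap.

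**The case against.** The strongest reply is that the wording is loose rather than wrong. The next sentence says that experienced surgeons' data are not stratified, which suggests that roll-in data are. The whole cohort may then mean patients across the study rather than only that surgeon's later cases. That reading is possible, but the text does not state it, and Section 12 does not supply it.

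A second reply is that the effect may be trivial. Prior RAVINE experience is the stated criterion and roll-in is the exception. With three roll-ins the shrinkage is 1.4%, with 15 it is 6.8%, and the larger scenarios need a new surgeon at every site. The factor 1 − m/N can also be undone by any reader who knows m. This is fair, and it limits the size of the point. It does not make the diluted contrast the right one to report.

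A reader might go further and infer that the check has a faulty type I error and low power. The documents do not support that as a fact. They name no test, and a descriptive table or an overlap-corrected variance would have no such fault. The error rates in Step 3 apply only if the groups are treated as independent samples.

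A reader might also infer that the check decides whether early cases are pooled into the 24-month result. No section says so. The only poolability statement, in Section 12.8, concerns sites.

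**Conclusion.** The point holds in a limited form. On the literal wording the comparator includes the roll-ins, and the reported difference is diluted by exactly 1 − m/N: negligible with a few new surgeons, about 20% with 45 roll-ins, about 40% with 90. That part is algebra. Its size rests on the assumed m and on roll-ins counting in the 222, neither of which the documents settle.

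The loss of power (about 72% against 85% for m = 45) is conditional on a test that the plan does not name, and on the assumed 1.0-point difference and two-sided 0.05. Where it arises, it makes a real learning curve easier to miss; it does not create a false one.

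It would be wrong to read this as a flaw in the primary analysis. The one-sample tests against 3.25 and the sample size of 222 do not depend on this check. The correction is worth making because the stated comparison understates what it looks for and is easy to put right.

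**What to change.** - In the synopsis and Section 3, name all non-roll-in patients as the comparator in place of the whole cohort.
- In Section 12, state that these disjoint groups are compared on 24-month Back and Leg VAS change and on complication incidence, and name the method.
- Where numbers allow, add a comparison with the same surgeons' later patients. The non-roll-in group also contains experienced surgeons' cases, so the main contrast mixes early experience with differences between surgeons.
- State whether roll-ins count in the 222, in the ITT population and in the Per-Protocol population, and report how many there were.
- Report the primary one-sample tests with and without roll-ins as a sensitivity analysis.

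The cost is one phrase in two places, a short addition to Section 12 and one extra table. No new data are needed.
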